### 3.2.2.2 Countermovement Jump

The participant begins in a standing position with feet shoulder-width apart and arms relaxed. Upon initiation, the athlete rapidly performs a countermovement by flexing the hips and knees to approximately 90° between the trunk and thighs, followed by explosive vertical propulsion through coordinated hip and knee extension, synchronized with upward arm swing to ear level (Hou et al., 2025). During the airborne phase, the body remains upright, and upon landing, the athlete transitions from forefoot to full-foot contact while maintaining stability, with post-landing knee flexion limited to  $\leq 30^\circ$  to minimize impact forces (Morin et al., 2011) (see Figure 5 for movement breakdown).

[figure not shown]
Force plates are utilized to record ground reaction forces (GRF) across all phases (countermovement, takeoff, and landing) (Myer et al., 2008). Jump height is calculated via the impulse-momentum method by integrating force-time data from the countermovement phase to takeoff (Weyand et al., 2000). Key parameters—including rate of force development (RFD), peak force magnitude, force-time curve symmetry, and force attenuation gradients during the initial 200 ms of landing—are analyzed to quantify lower limb stiffness, neuromuscular coordination, and dynamic stability. Notably, landing-phase force decay patterns correlate with knee joint stability and serve as predictive indicators of injury risk (Higashihara et al., 2018; Myer et al., 2011).

Figure 5 Countermovement Jump

### 3.2.2.3 Single - Leg Countermovement Jump

Participants stand on one leg on a force platform, with the non-supporting leg flexed at approximately  $90^\circ$  at the knee and hands on hips to maintain an upright posture (Sharrock et al., 2011). At the start of the test, subjects perform a rapid countermovement by coordinated flexion of the hip and knee (with a trunk-thigh angle of approximately  $45^\circ$ ), followed by an explosive single-leg extension to jump vertically, synchronizing arm swing to enhance momentum. During the aerial phase, a neutral pelvic position must be maintained. Upon landing, subjects make contact with the forefoot and maintain knee flexion  $\leq 25^\circ$ , avoiding compensatory trunk tilt or swinging of the non-supporting leg throughout the movement (Hibbs et al., 2008), the decomposed movements are shown in Figure 6.

### **3.2.3 Skills Measurement**

#### **3.2.3.1 Biomechanical Application and Kinematic Analysis of Motion Markers**

This study will employ the TecnoBody D-WALL 3D motion capture system, which is equipped with 12 cameras operating at a frequency of 200 Hz. The system will track retroreflective markers, whose placement strictly adheres to the standards established by the International Society of Biomechanics (ISB) (Wu et al., 2002). As illustrated in (Table 12, Figure 7a and 7b), these markers will be precisely positioned at key joint sites of beginner female gymnasts, including the ankle, knee, hip, shoulder, elbow, and wrist joints, as well as the thoracic and lumbar spine regions. As emphasized by Sadeghi et al., (2021), this meticulous marker placement is designed to comprehensively capture detailed movement patterns.

Given that all subjects are female, the process of attaching markers will be exclusively carried out by female researchers. Additionally, the subjects are required to wear gymnastic uniforms and gymnastic shoes during the test. A comparative analysis of the subjects' performance before and after the intervention will be conducted, with a primary focus on evaluating stability during rotational movements and jumping skills. This aligns with the research direction of Pupo et al., (2012). This methodology will facilitate a profound understanding of how interventions impact the gymnasts' performance in these critical movement segments.

Table 12: Marker Positions and Names

Body Part	Marker Position	Marker Code
Head	On the head, above the left/right ear.	A1/A2
	On the head, at the front center.	A3
Trunk	Superior end of sternum	B1
	Spinous process of second thoracic vertebra	B2
	Spinous process of tenth thoracic vertebra	B3
	Left/Right 12th Rib	B4/B5
Upper Limb	Left/Right Acromion	C1/C2
	Left/Right Lateral Epicondyle of Humerus	C3/C4
	Left/Right Medial Epicondyle of Humerus	C5/C6
	Left/Right Styloid Process of Radius	C7/C8
	Left/Right Styloid Process of Ulna	C9/C10
	Left/Right Head of 2nd Metacarpal	C11/C12
Pelvis	Left/Right Anterior Superior Iliac Spine	D1/D2
	Left/Right Posterior Superior Iliac Spine	D3/D4
	Left/Right Highest Point of Iliac Crest	D5/D6
	Midpoint between Spinous Processes of L4 and L5	D7
Lower Limb	Left/Right Thigh Point	E1/E2
	Left/Right Lateral Condyle of Femur	E3/E4
	Left/Right Medial Condyle of Femur	E5/E6
	Left/Right Anterior Leg (Tibial Tuberosity)	E7/E8
	Left/Right Lateral Malleolus	E9/E10
	Left/Right Medial Malleolus of Tibia	E11/E12
	Left/Right Heel Point (at the Same Height as Toe Point)	E13/E14
	Left/Right 1st Metatarsal Point	E15/E16
	Left/Right 5th Metatarsal Point	E17/E18
	Left/Right Toe Tip (Midpoint between 2nd and 3rd Metatarsal)	E19/E20

[figure not shown]
[figure not shown]

Figure 7a Placement of marker attachment on participants. The red points in the diagram indicate the joint areas where marks need to be pasted.

[figure not shown]
[figure not shown]

Figure 7b The marker that will be used to attached on the participant's body. Marks are typically reflective materials or high-contrast stickers applied to key observation sites on athletes' bodies (e.g., joints or motion-sensitive areas) for biomechanical analysis. These visual markers assist technical devices such as cameras and sensors in precisely tracking body movement trajectories by providing distinct visual references, enabling accurate capture of motion patterns for performance

### 3.2.3.2 Measurement of Straight Jump 360° Turn

Participants start in an upright position with feet together and arms raised overhead. During the test, they swing their arms backward, perform a natural squat, and execute an explosive vertical jump upward, synchronizing arm movement to generate momentum. Upon reaching the aerial phase, subjects rapidly engage core muscles to complete a 360° horizontal rotation around the vertical axis, maintaining stable head and gaze direction to control the rotation axis. When landing, contact is made first with the forefoot, transitioning to full-foot support, while maintaining knee flexion  $\leq 30^\circ$ , avoiding lateral hip displacement, and keeping the trunk upright to absorb impact forces (Joseph, 2012). The entire movement must ensure continuity among the takeoff, rotation, and landing phases, with no loss of balance or deviation in the rotation axis, the decomposed movements are shown in Figure 8.

#### 3.2.3.2.1 Center of Gravity Deviation

The athlete executes a two-leg takeoff and completes a 360° aerial rotation around the hip joint as the axis, requiring the maintenance of body balance upon landing. During the test, this metric is defined as the maximum distance by which the three-dimensional displacement of the center of gravity (COG) deviates from the ideal rotational path (Hechenblaikner, 2024). Dynamic Balance Control: Smaller values indicate stronger ability of the central nervous system to

regulate aerial posture and higher landing stability. Biological Explanation: The mechanical model is expressed as

$$D = \sqrt{(X \text{ real} - X \text{ ideal})^2 + (y \text{ real} - y \text{ ideal})^2 + (Z \text{ real} - Z \text{ ideal})^2}$$

where X, Y, Z represent the actual COG coordinates versus the ideal trajectory coordinates (Etkin & Reid, 1995).

### **3.2.3.2.2 Joint Angle Variation**

Student participants need to analyze angular fluctuations of hip, knee, and ankle joints during the aerial phase of two-footed vertical jumps with rotation. These fluctuations serve as crucial performance indicators: A coefficient of variation (CV) below 8% (professional athlete standard) suggests efficient lower limb coordination, while CV exceeding 12% typically indicates compensatory muscle strategies (e.g., excessive quadriceps activation may increase patellar tendon stress) (Cazzola et al., 2016). Angular fluctuations also serve as an energy loss indicator, positively correlated with muscular work through the theoretical model  $E_{\text{loss}} = k \cdot \Delta\theta^2$  (Ditroilo et al., 2011). For measurement, 200Hz high-speed cameras will capture joint angular velocity curves to calculate CV. Elevated CV values reflect insufficient hamstring-gluteal complex stiffness, indicating the need for targeted strength and neuromuscular coordination training.

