### **1.3 RESEARCH QUESTIONS**

- (1) What are the differential effects of static, dynamic, and static-dynamic combined balance training on the stability (measured by the maximum distance of single-leg extension and the bilateral symmetry index in the Star Excursion Balance Test (SEBT)) of beginner gymnasts?
- (2) Do static, dynamic, combined balance training induce distinct improvements in jumping mechanics (CMJ/SLCMJ: jump height, PF, RFD, impulse) and kinetic efficiency (jump height/GRF ratio), and does combined training show superior neuromuscular adaptations?
- (3) Among static, dynamic, and static-dynamic combined balance training modalities, which one most effectively minimizes the center of mass (COM) offset distance, body sway amplitude, and landing impact force—while maximizing rotational smoothness and single-leg balance duration—in beginner gymnasts when they perform 360° single-leg standing pirouettes and 360° straight-body jump turns, with all outcomes quantified by 3D motion capture technology?

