Impulse:	In countermovement jumps, impulse is the accumulation of ground reaction force (GRF) over time (the area under the force-time curve) (Claudino et al., 2017). Its net impulse (total impulse minus gravitational impulse) determines the change in human momentum, directly dictating the takeoff velocity and jump height (Painter et al., 2022).
Center of gravity deviation distance	In rotational movements, the center of gravity deviation distance refers to the perpendicular deviation distance of the center of gravity (CoG) relative to the rotation axis—the smaller the deviation, the higher the efficiency of rotational control (Lee et al., 2021).
Joint Angle variation	It refers to the dynamic angular changes in each joint relative to the initial posture, which regulates the moment of inertia and angular momentum by adjusting joint flexion/extension to achieve precise control over rotational speed and stability (Moke et al., 2020).

Vertical Jump Efficiency	It refers to the ability to convert energy generated by muscle contraction (especially the elastic energy stored during the eccentric-concentric contraction cycle and the energy from active force generation) into the gravitational potential energy required for the vertical displacement of the body's center of mass (Kazuaki et al., 2022).
Landing Impact Force	It refers to the instantaneous peak force generated by the ground reaction force (GRF) now the body contacts the ground (Mojaddarasil & Sadigh, 2021a).
Body Oscillation Amplitude	It refers to the maximum displacement of the body's center of mass (or specific segments) relative to the equilibrium position during dynamic movements such as running, jumping, and walking (Pettorossi et al., 2013).
Rotation Smoothness Index	It is a quantitative index used to evaluate the smoothness of the angular velocity time series in rotational movements (such as gymnastic twists and figure skating spins) (Sjölander et al., 2008).

## CHAPTER 2

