Stand with your feet shoulder-width apart, lean your body slightly forward, and bend your knees into a half-squat position (ensure your knees do not go past your toes and your hips are pushed back), while engaging your core muscles to maintain stability. Then, explosively push through your feet and use coordinated arm swings to jump upward as high as possible. When landing, gently absorb the impact by bending your knees and smoothly returning to the half-squat position to keep your body balanced.

Training recommendation: Perform 10 repetitions per set, and complete 3 sets in total.

Figure 3m Jump training

The subject assumes an upright posture (with the body stiff and straight like a "straight stick", core engaged, and no torso bending), pushes off with one or both feet to jump, completes a 360-degree horizontal rotation in the air around the body's longitudinal axis, while keeping the body fully extended and limbs fixed (such as arms pressed tightly against the torso or maintaining a specific pose), and finally lands smoothly on both feet, with the body still maintaining upright stability upon landing.

Figure 3n Jumping with rotation

Stand on one foot, extend and lift the other leg straight backward and upward (with toes pointed), lean the upper body forward until it is parallel to the ground or lower, and naturally spread the arms (such as in lateral or forward raises) to maintain balance. It requires the standing leg to stay straight and stable, the lifted leg and upper body to form a straight line, the core to be engaged, and the eyes to look forward or at the ground, demonstrating flexibility and balance.

Figure 3o Swallow balance

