### 3.8.2.3 TecnoBody 3D Motion Capture System (gymnastic performance movements)

To accurately assess the biomechanical parameters of the 360° straight jump turn and single-leg standing rotation, experimental procedures must integrate standardized protocols with real-time interaction: Test operators first instruct participants to stand still while reflective markers are affixed to anatomical landmarks (acromion, anterior superior iliac spine, greater trochanter, and lower limb joints), emphasizing that "markers must align with bone structures—avoid movement to prevent displacement (Soylu et al., 2025). During static calibration, participants are directed to stand naturally at the center of the force platform with arms relaxed and gaze forward, maintaining stillness for 10 seconds to establish the skeletal model. For formal testing, the straight jump turn requires execution under the command jump vertically, complete a 360° mid-air rotation, and land stably, while the single-leg rotation emphasizes upright posture on the support leg, stable trunk alignment, and 2-second balance maintenance post-rotation, with each movement repeated three times to ensure data reliability. During acquisition, the system provides real-time alerts such as "right knee marker

occluded—adjust arm posture and retest" or "insufficient rotational angular velocity—reduce trunk compensation," ensuring movement standardization. Coaches view screens displaying the participant's center of mass trajectory (red) overlaid with the ideal biomechanical model (green), accompanied by feedback like "0.2-second delay in hip extension—optimize takeoff sequencing." Post-test, data undergoes quality control screening (e.g., center-of-mass deviation standard deviation  $<1.5$  cm, marker occlusion rate  $<5\%$ ), encrypted and stored under the naming convention 'action-date' for subsequent biomechanical modeling and training optimization. This protocol, combining movement standardization, real-time correction, and multimodal data integration, enables granular analysis of rotational techniques (Bravi et al., 2023), supporting technical refinement and injury prevention research in disciplines such as artistic gymnastics and dance.

Figure 13(a) The 3D Motion Capture System

[figure not shown]

Figure 13(b) The Schematic placements of the motion capture system

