## 4.4 Gymnastics skills test results

### 4.4.1 Straight jump 360 ° turn test results

Table 19 Straight jump 360 ° turn test results at baseline and 8 weeks postintervention in the static intervention, dynamic intervention, static-dynamic intervention, and control groups. Data presented as mean  $\pm$  SD.

Group	Test Type	Time Point	Center of gravity deviation distance	Joint Angle variation (°)	Vertical Jump Efficiency (%)	Landing Impact Force (N)	Two-Way Repeated Measures ANOVA	Bonferroni (p)
Static balance group	Straight jump 360 ° turn (Pre-Test)	B						
		W8						
	Straight jump 360 ° turn (Post-Test)	B						
		W8						
Dynamic balance group	Straight jump 360 ° turn (Pre-Test)	B						
		W8						
	Straight jump 360 ° turn (Post-Test)	B						
		W8						
Static and Dynamic balance group	Straight jump 360 ° turn (Pre-Test)	B						
		W8						
	Straight jump 360 ° turn (Post-Test)	B						
		W8						
Control group	Straight jump 360 ° turn (Pre-Test)	B						
		W8						
	Straight jump 360 ° turn (Post-Test)	B						
		W8						

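### Joint angle variation in the straight jump turn is defined in three incompatible ways, and its percentage cut-offs do not fit a coefficient of variation of angular velocity

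*Protocol*

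**What the plan says.** The protocol describes the outcome in three places.

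- **Section 1.6 (operational definition):** "It refers to the dynamic angular changes in each joint relative to the initial posture". This is an angle.
- **Section 3.2.3.2.2 (measurement):** the object is "angular fluctuations of hip, knee, and ankle joints during the aerial phase of two-footed vertical jumps with rotation". The measurement sentence is "200Hz high-speed cameras will capture joint angular velocity curves to calculate CV", and the scale is a percentage: "A coefficient of variation (CV) below 8% (professional athlete standard) suggests efficient lower limb coordination, while CV exceeding 12% typically indicates compensatory muscle strategies". The energy model in the same section uses the square of an angle change, not a velocity.
- **Table 19 in section 4.4.1 (planned results):** the column "Joint Angle variation" carries the unit degrees. It is one column, beside a two-way repeated measures ANOVA, although section 3.2.3.2.2 names three joints.

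Section 1.4.2, objective 3, lists the outcome as one of four for the straight jump turn. Section 1.3 calls the task "360° straight-body jump turns". For the matching training movement, section 3.2.1.3 asks for "keeping the body fully extended and limbs fixed". Section 3.8.2.3 has "each movement repeated three times to ensure data reliability".

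**The concern.** An outcome that enters a hypothesis test has to be a single variable. Here an analyst could compute an angle, a velocity-based percentage or some other quantity in degrees, and cite the protocol for each. A separate analysis plan could choose among them, but any choice would contradict at least one current section. If the choice is left until the data are in, it can be made with the results in view.

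The CV version raises a second problem. A CV divides by a mean. In a jump where the body is meant to stay straight, a joint may finish the flight near the angle at which it started, and its mean signed angular velocity is then small. The ratio may reflect the small denominator more than the movement quality it is meant to describe.

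**Working it through.** **Step 1. Compare the definitions.**

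| Place | Quantity | Unit | Joints |
|---|---|---|---|
| 1.6 | angle change from starting posture | an angle | each joint |
| 3.2.3.2.2 | CV from angular velocity curves | %, cut-offs 8 and 12 | hip, knee, ankle |
| Table 19 | joint angle variation | degrees | one column |

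An SD of velocity divided by a mean velocity has no unit, so the second row cannot produce the third. Section 3.2.3.2.2 also leaves open whether the CV is over time within a flight or across trials, whether velocity is signed or absolute, and how three joints and two sides become one value.

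**Step 2. Examine the within-flight, signed reading.** Let D be the net change of a joint angle over the flight, T the flight time and A the size of a mid-flight excursion. None of these is in the protocol. Assumed ranges: D 0.5° to 20°, A 2° to 10°, T 0.4 to 0.6 s.

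- Angle: θ(t) = D·t/T + A·sin(πt/T)
- Mean velocity: D/T
- SD of velocity: A·π/(√2·T)
- CV = SD/|mean| = A·π/(√2·|D|) = 2.22·A/|D|. T cancels.

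Evaluated at the protocol's 200 Hz:

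| A | D = 0.5° | 1° | 2° | 5° | 10° | 20° |
|---|---|---|---|---|---|---|
| 2° | 889% | 444% | 222% | 89% | 44% | 22% |
| 5° | 2221% | 1111% | 555% | 222% | 111% | 56% |
| 10° | 4443% | 2221% | 1111% | 444% | 222% | 111% |

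With A fixed at 5°, moving D from 1° to 2° halves the score.

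**Step 3. Check how stable a three-trial mean would be.** Simulation with T = 0.5 s, A averaging 5° (SD 1°), and D varying between trials with SD 2°:

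| Mean D | Median CV | 5th to 95th percentile |
|---|---|---|
| 0° | 1230% | 465% to 10354% |
| 2° | 772% | 306% to 6078% |
| 5° | 249% | 161% to 629% |
| 10° | 114% | 86% to 154% |
| 20° | 56% | 45% to 69% |

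The upper percentile is about 20 times the lower at a mean D of 2° (6078/306), about 4 times at 5° (629/161) and about 1.5 times at 20° (69/45). The instability belongs to small net changes.

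**Step 4. Compare with the cut-offs.** A CV below 8% needs A < 0.08/2.22·|D| = 0.036·|D|. Below 12% needs A < 0.054·|D|. Either means that the joint turns at nearly constant speed through the flight, which is not what a held posture looks like. With absolute velocity the ratio is bounded, at about 22% to 75% over the assumed ranges, and still lies above both cut-offs.

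**The case against.** The strongest reply is that the instability depends on a reading the protocol does not fix. With three repetitions, the CV could be taken across trials, for example of peak velocity, and that has no near-zero denominator. Absolute velocity removes the problem too. The wording about a fully extended body belongs to a training movement. The test description in section 3.2.3.2 gives no hip, knee or ankle angles in flight, and it asks for a forefoot-first landing with knee flexion of up to 30°. Beginners may well show net changes of 10° to 20°, where the ratio settles. All of this stands, so the instability has to be stated conditionally.

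Three stronger readings are tempting, and the documents do not support them.

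- A reader might infer that the coefficient is unstable as the protocol stands. That follows only for a signed, within-flight CV with small net joint change.
- A reader might infer that a gymnast who holds the body straighter would score worse. In the formula, if the excursion and the net change shrink together, the CV does not move. The inference needs net change to fall while the fluctuation does not.
- A reader might infer that the HA3 result for this outcome would be driven by the denominator. If the degrees of Table 19 govern, the CV never enters the ANOVA.

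None of this removes the conflict over definition and unit. An across-trial CV is not in degrees either.

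**Conclusion.** The definition is wrong as written. Sections 1.6 and 3.2.3.2.2 and Table 19 cannot all be followed, and this rests on the text alone.

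The criticism of the CV is secondary and conditional. On the signed, within-flight reading, net changes of 5° or less with excursions of 2° to 10° give values from 89% to 4443%. These figures are illustrative: they come from a simple sinusoidal model and assumed ranges. On either within-flight reading, signed or absolute, every value in the assumed ranges exceeds 12%, so the cut-offs would not separate good from poor performance there. An across-trial CV was not evaluated, and the protocol does not define one.

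The reach is limited: one of four outcomes for one of two movements under objective 3. It should be settled before data collection, which Table 22 dates 1/9/2026.

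**What to change.** Define the outcome once, in degrees. A workable choice is the range of joint angle (maximum minus minimum) during the aerial phase, computed separately for hip, knee and ankle and averaged over the three trials, with a stated rule for combining left and right sides. Reword section 1.6 and section 3.2.3.2.2 to match, and remove the angular-velocity CV and its 8% and 12% cut-offs. Give Table 19 one column per joint.

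The same motion-capture recordings serve, so no extra measurement is needed. The cost is more than wording, however: Table 19 gains two columns, and one test becomes three joint-level tests that must be counted in the multiplicity handling.
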